## **Overall Statistical Analysis Plan**

NIH funding will support a mixed methods study including a randomized controlled trial and qualitative research to evaluate the impact of CRx-D. This research will fill important gaps in knowledge about how to best leverage clinical care visits to identify, support and improve outcomes for ADRD caregivers and PWD. For each aim, we provide exemplary hypotheses.

Aim 1: Among ADRD caregivers who screen positive for one or more unmet HRSNs, we will evaluate the longitudinal effects of CRx-D versus usual care on caregiver self-efficacy (10 outcome) and 20 outcomes including: psychosocial (unmet needs, social isolation, well-being, burden, depression, stress), behavioral (resource use), and health and healthcare utilization. We will also examine effects of the intervention on care recipient well-being, resource needs and use, health and health care utilization (reported by caregiver as the proxy).

Hypothesis 1a. The intervention group will report higher levels of self-efficacy at 12 months compared to controls.

Hypothesis 1b. Caregivers in the intervention group and their care recipients will have fewer unmet needs and higher rates of community resource use at 12 months than controls and their care recipients.

Hypothesis 1c. Caregivers and PWD in the intervention group will have better health and well-being at 12 months than controls.

**RCT Strategy, Timeline, Methods, and Key Measures:** A consecutive sample of caregivers seeking care at UCMC will be enrolled Y1Q3-Y2. Eligible subjects will include patients who live in the target region, identify as an ADRD caregiver and agree to receive text messages from the research team (>98% of people screened for CRx-2 could receive texts). Recruitment will occur in three outpatient sites: primary care, gynecology and Senior Care – South Shore (SCSS). Researchers will consecutively approach patients in the waiting room, screen willing patients for eligibility and enroll eligible patients.

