The proposed sample size of 344 is sufficient based on a non-inferiority margin of 7.6 points in patient satisfaction (primary outcome) assuming group allocation 1:1, power=0.8, one-sided  $\alpha$ =0.025, standard deviation=25. The non-inferiority margin of 7.6 points is less than half of the standard deviation for mean transformed general satisfaction scores in a population-based sample (e.g., male [mean=65, SD=23], female [mean=64, SD=24]); half a standard deviation is considered a minimally important difference.

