We will also use survival analysis methods and methods for analyzing count data (e.g., Poisson or negative binomial regression) to explore acute and emergency healthcare utilization. For example, time from enrollment to first home EMS or ER visit will be calculated for each subject and those who never have one of these events will be censored at the end of study follow-up. Stratified Cox proportional hazards regression models will be fit with intervention group as the independent variable and clinical enrollment site as a stratification factor, due to the potential for different underlying rates based on clinical site. The proportional hazards assumption will be checked using log-log plots of survival and Schoenfeld residuals.

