#### Sample Size

Aim 2 analyses will include all caregivers enrolled in the trial (N=344). The non-inferiority margin of 7.6 points is less than half of the standard deviation for mean transformed general satisfaction scores in a population-based sample (e.g., male [mean=65, SD=23], female [mean=64, SD=24]); half a standard deviation is considered a minimally important difference. [Calculations assumed power=0.8, one-sided alpha=0.025, and standard deviation=25]

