### Analysis Plan

# *Aim* 1 Analytic Plan [Aim 1 analytic plan is included here because it was referenced in Aim 2 due to overlap)

To determine the impact of CRx-D on the highest risk group, Aim 1 analyses will focus on 172 caregivers with at least 1 HRSN. Descriptive statistics will be used to summarize, overall and by study arm, sociodemographic characteristics and primary and secondary outcomes at each measured time point. The mean, standard deviation, median, and inter-quartile range will be generated for continuous variables; frequency counts and percentages will be generated for categorical variables.

The main analyses will follow the principle of intent-to-treat, and include all 172 ADRD caregivers with at least 1 unmet HRSN in the study arm to which they were allocated.

To fully leverage the longitudinal data, generalized linear mixed-effects models (GLMM) will be fit with particular interest in the time (7, 30, 90 days and 12 months post-enrollment) by study arm interaction; baseline values will be included as a covariate. Based on this model, appropriate

contrasts to test the intervention effect at specific time points (e.g., 12 months) will be constructed. These contrasts will permit examination of early versus late intervention effects, valuable information for future iterations of this and other ADRD caregiver self- and family management interventions. GLMM can be used for continuous (e.g., mean caregiver self-efficacy for providing care score, patient satisfaction score, stigma score), ordinal (e.g., physical health of PWD by proxy) or binary (e.g., resource use, resource sharing) outcomes. Models will include covariates moderately associated with the outcome to remove differences attributable to baseline covariates and increase precision of the estimate of the treatment affect. Latent growth curve modeling is a viable alternative to GLMM and will be explored when sufficient variability in the distributions of patterns of outcomes by time points exist (e.g., with the binary outcomes there will be a limited number of potential patterns).

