We will use the analytic approach described for Aim 1 [above]. Here, we discuss analytic issues unique to Aim 2. To facilitate ease of interpretation of the primary outcome, we will linearly rescale the composite score for the PSQ-18 subdomain of general satisfaction (questions 3 and 17). Five possible responses for each of the two items are scored 1 to 5; with a higher score equating to higher satisfaction. Scores will be transformed using the formula: y = 100 \* (x-a)/(b-a) where y=the transformed score, x=the original score, a=the minimum possible score and b=the maximum possible score. Transformed items will be averaged to generate the composite score (range 0-100; [higher scores indicating greater satisfaction]). Of particular interest for the non-inferiority hypothesis will be the [95%] confidence interval for the difference (usual care - CRx-D) and whether or not the upper limit of the confidence interval exceeds the non-inferiority margin. Of note, superiority of the intervention with respect to [satisfaction or] stigma will also be tested as this can be done without penalty. Typically, analyses of patient satisfaction data adjust for case-mix (age, education and general health status); this will be feasible, but given the randomized design and single-site analysis, adjustment should not be necessary. In addition, to determine whether there are substantial differences in the intervention's effect on ADRD caregivers with unmet HRSNs compared to ADRD caregivers without unmet HRSNs, the intervention by unmet HRSNS interaction will be tested. As in Aim 1, we will examine for differential intervention effects on primary and secondary outcomes among racial and ethnic groups, and by sex, using effect modification

analyses. Some analyses will be restricted to the group without HRSNs (N=172) to provide a more complete assessment of the impact of the intervention on this group (e.g., incidence of unmet HRSNs over time).

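### Aim 2 sets aside case-mix adjustment for satisfaction for a reason that covers bias but not precision, a missed efficiency gain in a valid analysis

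*SAP*

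**What the plan says.** The Aim 2 part of the Analysis Plan (SAP, Aim 2 Statistical Analysis Plan) notes that satisfaction analyses usually adjust for case-mix, names age, education and general health, and says this could be done here. It then gives its reason for not doing so: "given the randomized design and single-site analysis, adjustment should not be necessary". The same sentence stands in the Overall Statistical Analysis Plan.

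The Aim 2 entry under Additional Information, Clarification, Changes writes out the non-inferiority model for satisfaction and for discrimination: an intercept, a treatment indicator and an error term. It has no covariates and no term for the randomisation stratum, although the Overall Statistical Analysis Plan stratifies randomisation by unmet HRSNs (0 versus at least 1).

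Non-inferiority is judged by whether the upper 95% limit for usual care minus CRx-D exceeds 7.6 points on a 0 to 100 scale. On the sample size, the Aim 2 Sample Size section records: "Calculations assumed power=0.8, one-sided alpha=0.025, and standard deviation=25".

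**The concern.** Randomisation makes the unadjusted difference unbiased, and recruiting within one institution limits variation between centres. Neither says anything about how wide the interval is. A baseline variable that predicts satisfaction leaves avoidable residual variance when it is left out, even with perfectly balanced arms. The SAP does not weigh this, although the Aim 2 decision rests on one confidence limit.

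The stratum is a related omission. If unmet need at baseline is related to satisfaction, a model without it counts between-stratum variation as noise, although stratified randomisation has already balanced that variation between the arms.

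What is at stake is the chance of failing to show non-inferiority when the intervention truly does no harm to satisfaction. The validity of the estimate is not at stake. The design has little slack: the Aim 2 calculation states no allowance for dropout.

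**Working it through.** **Inputs.** Margin 7.6, SD 25, one-sided alpha 0.025 and power 0.80 (SAP, Aim 2 Sample Size); N = 344 with 1:1 allocation, so 172 per arm (Overall Statistical Analysis Plan). True difference taken as 0. The documents give no R² for the covariates, so a range is assumed.

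**1. Reproduce the plan's figure.**
n per arm = 2 × 25² × (1.96 + 0.8416)² / 7.6² = 1250 × 7.849 / 57.76 = 169.9, rounded up to 170. The total is 340, against 344 in the plan. The plan's number reproduces without any adjustment.

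**2. Unadjusted analysis at 172 per arm.**
SE = 25 × √(2/172) = 2.70
Half-width = 1.96 × 2.70 = 5.28
Power = Φ(7.6/2.70 − 1.96) = Φ(0.86) = 80.5%

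**3. Adjusted analysis.** Residual SD = 25 × √(1 − R²), put through the same formulas:

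| Assumed R² | Residual SD | Half-width | Power |
|---|---|---|---|
| 0 (unadjusted) | 25.00 | 5.28 | 80.5% |
| 0.02 | 24.75 | 5.23 | 81.3% |
| 0.05 | 24.37 | 5.15 | 82.4% |
| 0.10 | 23.72 | 5.01 | 84.4% |
| 0.15 | 23.05 | 4.87 | 86.4% |

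**4. Cost if the covariates predict nothing.** With three case-mix terms the interval widens by a factor of about √(341/338) = 1.004, or 0.4%. A fourth term for the stratum takes this to at most √(341/337) = 1.006.

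**5. With some loss.** At an assumed 10% loss (172 × 0.9 ≈ 155 per arm), SE = 25 × √(2/155) = 2.84 and unadjusted power is 76.3%. With R² = 0.10, the residual SD of 23.72 gives power of 80.5%, about the level with complete data and no adjustment.

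**The case against.** The strongest answer is that nothing is broken. The unadjusted estimate is unbiased, the sample size reproduces, and power is 80.5% on the plan's own inputs. The SAP says only that such adjustment is usual. It does not show that these variables predict satisfaction in these caregivers. At R² = 0.02 the gain is under one percentage point of power, and at R² = 0.10 the half-width shrinks by 0.27 points on a 0 to 100 scale. All of this stands, and it is why the point is one of efficiency.

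A reader might infer more from the text in two places.

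- *That the single-site premise is false.* The Overall Statistical Analysis Plan says "Recruitment will occur in three outpatient sites", and the Aim 1 Analysis Plan stratifies its Cox models with "clinical enrollment site as a stratification factor, due to the potential for different underlying rates based on clinical site". But the three sites are clinics of one institution, and Protocol section K says the trial is not multi-site, so the phrase can fairly mean one institution. The Cox models concern emergency care use in Aim 1, not satisfaction. The further hospital appears only in the protocol's change log, under the amendment for the 50 additional men, who are outside the Aim 2 N of 344.
- *That Aim 2 contradicts itself.* The Aim 1 approach that Aim 2 takes over says "Models will include covariates moderately associated with the outcome", partly for precision. But the Aim 2 text then turns to issues specific to Aim 2 and states its exception, and the clarification writes out a model that agrees with that exception. The covariate sentence also belongs to the longitudinal models, while satisfaction is measured once. A stated exception is not a contradiction.

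A last objection concerns timing. The SAP says in the past tense that data were analysed and that sensitivity analyses were performed. Changing the primary model after results are known would be a worse fault than a slightly wide interval. This stands and limits the fix.

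**Conclusion.** The concern holds as a missed efficiency gain. The reason given for not adjusting answers the question of bias and leaves precision unaddressed, and the model also omits the stratum used in randomisation. The unadjusted analysis is valid and reaches its stated power if data are complete.

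For R² between 0.02 and 0.15 the half-width would fall from 5.28 to between 5.23 and 4.87, and power would rise from 80.5% to between about 81% and 86%. These figures rest on SD 25, 172 per arm, a true difference of zero, and an R² that is assumed. It cannot be said that the interval is wider than necessary, only that it will be if the covariates are prognostic. The possible loss from adjusting is about 0.4% of the interval's width, so the balance favours adjusting where it can still be prespecified.

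**What to change.** Replace the sentence that calls adjustment unnecessary. In the Aim 2 regression for satisfaction and discrimination, prespecify age, education, baseline general health and the HRSN stratum (0 or at least 1) as covariates, and report the unadjusted model as a sensitivity analysis. Name the general health measure, and confirm that it is collected before the intervention is delivered. Keep the discrimination margin of 0.3 SD tied to the unadjusted SD, so that adjustment does not also shrink the margin.

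If outcome data have already been analysed, as the SAP's wording suggests, keep the unadjusted model as primary and add the adjusted model as a sensitivity analysis, labelled as specified after the fact.

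The cost is a few lines of SAP text and one further model. The SAP itself calls the case-mix adjustment feasible, and the stratum is known from randomisation. The downside is a few missing covariate values, which the multiple imputation already named in the plan can handle.

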## Handling of Missing Data

We aim to minimize missing data by employing interviewer-administered surveys and communicating to participants the protections of a Certificate of Confidentiality. Using these strategies, item non-response ranged from 0-3% in the CRx-2 trial. To avoid potential bias due to missing data, analyses will be conducted using multiple imputation with the chained equations method or inverse probability weighting to account for dropout and/or item non-response. In addition, characteristics of caregivers who complete each follow-up survey will be compared to caregivers who do not.

## Additional Information, Clarification, Changes

### September 2022

For each Aim, there is a single primary outcome, and no multiplicity adjustment will be made to the analyses of the secondary outcomes.

## Aim 2:

Since the non-inferiority margin of 7.6 for satisfaction with care is a relative effect size of 0.3 standard deviations, this relative effect size will be used as the non-inferiority margin for the secondary outcome of discrimination.

More formally, non-inferiority testing will use linear regression:  $Y = \beta 0 + \beta 1 * T + \varepsilon$ , where Y is the outcome (satisfaction with care or discrimination) and T is the treatment group indicator. The 95% CI for  $\beta 1$  will be of particular interest.

Since a majority of participants were female and African American or Black, formal interaction testing was not performed. However, a sensitivity analysis was performed that restricted analyses to females.

An additional sensitivity analysis was performed that restricted the analysis to those who selfcompleted the 1-week survey online (vs. via phone interview).

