We will also use survival analysis methods and methods for analyzing count data (e.g., Poisson or negative binomial regression) to explore acute and emergency healthcare utilization. For example, time from enrollment to first home EMS or ER visit will be calculated for each subject and those who never have one of these events will be censored at the end of study follow-up. Stratified Cox proportional hazards regression models will be fit with intervention group as the independent variable and clinical enrollment site as a stratification factor, due to the potential for different underlying rates based on clinical site. The proportional hazards assumption will be checked using log-log plots of survival and Schoenfeld residuals.

For the primary outcome (self-efficacy for providing care at 12 months) a sample of 86 caregivers/arm allows for detection of an intervention group difference of 0.43 points (sample size calculation using a group allocation of 1:1; power=0.8;  $\alpha$ =0.05, mean=2.8 and SD=1). With this sample size, power is sufficient to see at least a half a standard deviation (SD) difference in caregiver self-efficacy between intervention and control groups; half a standard deviation is considered a minimally important difference. Assuming 25% attrition, we will still be able to detect a difference equal to half an SD. Attrition in the pragmatic CRx-2 trial was 20%; this was an even lower-intensity intervention with no ongoing resource support nor touchpoints between follow-up surveys. In higher-intensity caregiver support studies, attrition rates range from 4% (MIND Study at 18 months) to 10% (REACH-II Study at 6 months). We will follow all caregivers through 12 months even if they no longer care for the PWD.

**Aim 2.** Among all ADRD caregivers (those who do and do not screen positive for unmet HRSNs), evaluate acceptability of the intervention as well as the effects of CRx-D plus usual care versus usual care alone on the health care experience, including satisfaction with care (10 outcome), experiences of stigma during clinical care and likelihood of sharing community resource information with others.

Hypothesis 2a. Among intervention group participants, the CRx-D intervention will be acceptable to caregivers with and without unmet HRSNs.

Hypothesis 2b. There will be no evidence, comparing the intervention group to controls, that CRx-D decreases caregiver satisfaction with care or promotes caregiver stigma.

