**Analysis and Sample Size Justification** Physician concern about negatively impacting patient satisfaction or causing stigma are barriers to intervening to address unmet needs. To address these, we hypothesize that satisfaction with care will not be significantly diminished among caregivers randomized to CRx-D compared to those randomized to usual care. Aim 2 analyses will include all caregivers enrolled in the trial (N=344).

We will use the analytic approach described for Aim 1. Here, we discuss analytic issues unique to Aim 2. To facilitate ease of interpretation of the primary outcome, we will linearly rescale the composite score for the PSQ-18 subdomain of general satisfaction (questions 3 and 17). Five possible responses for each of the two items are scored 1 to 5; with a higher score equating to higher satisfaction. Scores will be transformed using the formula: y= 100 \* (x-a)/(b-a) where y=the transformed score, x=the original score, a=the minimum possible score and b=the maximum possible score. Transformed items will be averaged to generate the composite score (range 0-100). Of particular interest for the non-inferiority hypothesis (H2b) will be the confidence interval for the difference (usual care - CRx-D) and whether or not the upper limit of the confidence interval exceeds the non-inferiority margin. Of note, superiority of the intervention with respect to stigma, unmet needs and other outcomes will also be tested as this can be done without penalty. Caregiver satisfaction will be measured at 7 days following the baseline outpatient visit; no longitudinal analyses will be conducted for this outcome. Typically, analyses of patient satisfaction data adjust for case-mix (age, education and general health status); this will be feasible, but given the randomized design and single-site analysis, adjustment should not be necessary. In addition,

to determine whether there are substantial differences in the intervention's effect on ADRD caregivers with unmet HRSNs compared to ADRD caregivers without unmet HRSNs, the intervention by unmet HRSNs interaction will be tested. As in Aim 1, we will examine for differential intervention effects on primary and secondary outcomes among racial and ethnic groups, and by sex, using effect modification analyses. Some analyses will be restricted to the group without HRSNs (N=172) to provide a more complete assessment of the impact of the intervention on this group (e.g., incidence of unmet HRSNs over time).

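### Does the non-inferiority test for discrimination read the wrong end of the confidence interval?

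*SAP*

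**What the plan says.** - **The directional rule.** In the Aim 2 SAP (Analysis Plan, Aim 2), the paragraph that builds the PSQ-18 general satisfaction score takes the 95% confidence interval "for the difference (usual care - CRx-D) and whether or not the upper limit of the confidence interval exceeds the non-inferiority margin". The score is bracketed as "higher scores indicating greater satisfaction". The Overall SAP (Aim 2, Analysis and Sample Size Justification) has the same rule, introduced with "Of particular interest for the non-inferiority hypothesis (H2b) will be the confidence interval".
- **The hypothesis.** Hypothesis 2b in the Overall SAP expects no evidence that "CRx-D decreases caregiver satisfaction with care or promotes caregiver stigma".
- **The discrimination scale.** Aim 2 SAP, Experiences of Discrimination: the Discrimination in Medical Settings Scale (DMS) is measured on day 7, runs from 7 to 35, and a higher score means more frequent discrimination.
- **The later addition.** Aim 2 SAP, Additional Information, Clarification, Changes: the 7.6-point satisfaction margin is expressed as 0.3 SD, and "this relative effect size will be used as the non-inferiority margin for the secondary outcome of discrimination". One linear model then serves both outcomes, "where Y is the outcome (satisfaction with care or discrimination) and T is the treatment group indicator", and the 95% interval for β1 is to be examined.

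**The concern.** The two scales run in opposite directions. A single rule that always reads the upper limit of the same difference cannot protect against harm on both. The plan states such a rule once, for usual care minus CRx-D. It then puts discrimination into the same non-inferiority framework without saying which arm T marks, what sign the margin has or which limit decides. An analyst who reused the stated rule for the DMS would become more likely to claim non-inferiority as CRx-D made discrimination worse, and less likely as CRx-D made it better. Stigma is half of the no-harm hypothesis, so a wrong tail there would matter.

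**Working it through.** **1. The plan's own figure.** Inputs from the Overall SAP, Aim 2 sample size: margin 7.6, SD 25, one-sided α 0.025, power 0.80, allocation 1:1.

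n per arm = 2 × [25 × (1.960 + 0.842) / 7.6]² = 169.9, so 170 per arm and 340 in total, against 344 stated. With 172 per arm, power is Φ(7.6 / (25 × √(2/172)) − 1.960) = 80.5%. The design figure reproduces. The relative margin is 7.6/25 = 0.304, which the SAP rounds to 0.3.

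**2. The stated rule, applied to satisfaction.** At a true deficit of 7.6 points, the chance of declaring non-inferiority is Φ((7.6 − 7.6)/SE − 1.960) = 2.5%. The rule is right where it is written.

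**3. The same rule copied to the DMS (hypothetical).** Let d be the true CRx-D minus usual care difference in SD units, so that positive d is harm. With 172 per arm, SE = √(2/172) = 0.1078.

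- Copied rule (upper limit of usual care − CRx-D below 0.3): P = Φ((0.3 + d)/SE − 1.960)
- Harm direction (upper limit of CRx-D − usual care below 0.3): P = Φ((0.3 − d)/SE − 1.960)

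| True rise d (SD) | Copied rule | Harm direction |
|---|---|---|
| 0 | 79.5% | 79.5% |
| 0.1 | 96.0% | 45.8% |
| 0.2 | 99.6% | 15.1% |
| 0.3 | 99.98% | 2.5% |

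For true falls of the same size the two columns swap. With 129 per arm, the contrast at a rise of 0.3 SD is 99.8% against 2.5%. That case assumes that the SAP's 25% attrition, stated for the 12-month outcome, also applies on day 7.

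**4. Does the coding of T change the answer?** With the usual coding, T = 1 for CRx-D, β1 is CRx-D minus usual care. Harm on the DMS is then a positive β1 and the upper limit decides. Harm on satisfaction is a negative β1 and the lower limit against −7.6 decides, which is the stated satisfaction rule with its sign turned. With the opposite coding both limits swap. Either way, once the harmful direction is known, the decision for each outcome is the same. The wrong tail arises only if the analyst also carries over the usual care minus CRx-D subtraction from the satisfaction paragraph.

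**5. Is the harmful direction known?** Set side by side:

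- Hypothesis 2b names promotion of stigma as the harm.
- The Aim 2 SAP Introduction gives the purpose as showing that CRx-D neither lowers satisfaction nor harms caregivers relative to usual care.
- The DMS scoring note says that higher is worse.
- Non-inferiority means not unacceptably worse.

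These allow one reading: exclude a rise of 0.3 SD in the CRx-D arm. No passage supports claiming non-inferiority because discrimination rose.

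**The case for a change.** The strongest case for a change has three parts. First, the Overall SAP attaches the upper-limit rule to Hypothesis 2b as a whole, and that hypothesis covers stigma. Secondly, the later section derives the discrimination margin from the satisfaction margin and opens its shared model with "More formally, non-inferiority testing will use linear regression", so it presents itself as the formal version of the earlier test. Thirdly, a pre-specified decision should not depend on inference, and a sentence or two would settle it.

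The first part is weak. The rule sits in the paragraph that defines the satisfaction score, next to the aim that "satisfaction with care will not be significantly diminished among caregivers randomized to CRx-D", and 7.6 satisfaction points is the only margin given with it. The Aim 2 SAP repeats the rule without the Hypothesis 2b label. In both places stigma appears separately, in the sentence on superiority. The second part cuts both ways: the formal version is an interval for β1, and under the usual coding its upper limit is the correct one for discrimination.

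The third part stands in a limited sense. The coding of T, the limit for each outcome and the SD that turns 0.3 into DMS points are not written down. These are details that analysts fill in the ordinary way. Using 0.304 instead of 0.3 moves the error rate at a true rise of 0.3 SD only from 2.5% to 2.7%.

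**Conclusion.** The concern does not call for a change. The plan lacks notation for one secondary outcome, but it contains no wrong rule. The 99.98% against 2.5% contrast is arithmetically correct. It describes an analyst who keeps the satisfaction subtraction and also disregards Hypothesis 2b and the DMS scoring note. An analyst who follows the plan reaches the harm-direction test, with an error rate of 2.5% at the margin and power of 79.5% when there is no difference. Those figures assume 172 analysed per arm and a margin of exactly 0.3 SD. The two-sided 95% interval that the plan reports would also show any reversal of sign. The satisfaction rule, its 7.6-point margin and the total of 344 are unaffected. Writing out the coding would not alter any test that the plan leads to.
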